1. INTRODUCTION

“Initiation of a novel In-Hospital Treatment for Patients with Type 2 Diabetes (REMIT-2-D)”

This study will implement and rapidly optimize an in-hospital treatment package for people admitted to the Lyell McEwin Hospital (LMH), The Queen Elizabeth (TQEH) and Royal Adelaide (RAH) Hospitals with Type 2 Diabetes Mellitus (T2DM). In-hospital educational resources to develop diabetes-related health literacy have been shown to be of benefit and there are advantages to a healthy eating and exercise pattern.¹⁻⁹ Our aim is to test a simple, effective treatment package that can be delivered by non-doctor or non-nurse personnel but who are suitably trained in the delivery of the educational resources. The focus is on health literacy to improve self-care and connect to community support. We know that a comprehensive package is of benefit, but we don't know which components of the package drive the benefit.

The study is the second stage of the MRFF funded “Reducing Morbidity Mortality and Costs by Initiation of a novel In-Hospital Intervention for Patients with T2DM (REMIT-2-D)” project. Stage one of the REMIT-2-D project comprised: (i) an analysis of the patterns of admission, length of stay and re-admission of people with T2DM to the Lyell McEwin, The Queen Elizabeth and Royal Adelaide Hospitals; (ii) a systematic review of in-hospital interventions to improve outcomes for people with T2DM; (iii) focus groups with Aboriginal and Torres Strait Islander people who have T2DM and those who provide health care services to them and (iv) a more general group of health care professionals who provide services to people with T2DM.

In stage two of the REMIT-2-D project we have developed a set of initial best guess informed by stage one and using a process of adaptive randomized design propose to undertake a pilot trial to establish (i) which of these interventions if any, is most effective to improve Glycated Haemoglobin (HBA1c) a measure of overall control of blood sugar, (ii) reduce diabetes related distress and (iii) the psychosocial, environmental factors and other health related factors that affect an optimal outcome being achieved. In addition, we plan to conduct a data linkage analysis to measure late (12 months) readmission to hospital and if readmitted, length of stay. This is included in the protocol and is part of the patient information and consent, however our grant timeline means that we may not complete this by the due date (June 2021) and thus request from this committee to extend the timelines of approval for an extra two years to allow time for the data linkage analysis.

2. BACKGROUND

The Initiation of a novel In-Hospital Treatment for Patients with Type 2 Diabetes (REMIT-2-DS2) Project is one of several projects to receive funding in 2018 for one year through approved disbursements from the Medical Research Future Fund (MRFF) under its Rapid Applied Research Translation Program. The REMIT-2-DS2 project is the second stage of the “*Reducing Morbidity Mortality and Costs by Initiation of a novel In-Hospital Treatment for Patients with T2DM (REMIT-2-D)*” project, which received funding from the MRFF in 2017.

Type 2 Diabetes (T2DM) is a chronic condition that effects a large and growing proportion of the world's population. In Australia, it is the fastest growing chronic condition, increasing at a faster rate than other leading chronic diseases such as heart disease and cancer.¹⁰ The Australian Institute for Health and Welfare found that prevalence of T2DM tripled between 1989/90 and 2014/15 with around 1.2 million known and registered Australians currently living with diagnosed T2DM, and an estimated additional 500,000 people with silent, undiagnosed T2DM whilst indigenous Australian

adults are almost 4 times as likely to have T2D as their non-Indigenous counterparts.¹¹ If T2DM continues to rise at the current rates, it is estimated that up to three million Australians over the age of 25 years will have T2DM by the year 2025.¹²

There is a 50% risk the children of a parent with T2DM will have a genetic susceptibility to the condition. However, the risk of developing the disease is strongly related to excess stores of body fat (85 – 90% of all people with the disorder are overweight or obese), and strongly influenced by a range of psychosocial and lifestyle related factors¹⁰⁻¹³.

The complications of T2DM are serious and can include cardiovascular disease, stroke, kidney disease, limb amputation, depression, anxiety and blindness. Not only are the complications of T2DM preventable with good primary health care and in-hospital medical care, but the condition is preventable with appropriate lifestyle changes such as diet, exercise, smoking cessation, minimisation of alcohol consumption and stress management¹⁰.

Finding sustainable solutions to curb the ill health, disability, mortality and costs associated with T2DM is an increasingly urgent priority for South Australian health practitioners and policymakers. Appropriate management of T2DM early in hospital admission may shorten length of stay, decrease readmissions rates and reduce the risk of morbidity due to long term complications¹⁴.

Many people with T2DM have complex care needs because they have more than one health condition and require services across hospitals, general practice primary care, community services and social care. However, that care is often fragmented across the different services, resulting in poor outcomes and inefficient use of scarce resources.¹⁵ Hospitalization presents an opportunity to coordinate multidisciplinary care, identify and initiate support that patients require in managing T2DM, and to build the capacity of patients in managing T2DM.

South Australia (SA) has the highest percentage of population with T2DM in Australia affecting over 106,000 people (6% of the SA population). T2DM is most prevalent in Adelaide's north, is strongly associated with social disadvantage, lower health literacy, and among people with a lower sense of mastery over their lives. The northern suburbs also have the highest rates of potentially avoidable hospitalisations in SA¹⁵ and 25% of people with T2DM in SA are re-admitted to hospital within 30 days, especially if they have co-morbid Cardiovascular Disease (CVD)⁷

Studies have found that 'recent' hospitalization is a risk factor for patient re-hospitalization unless discharge planning is adequately targeted to specific conditions, which may reduce unplanned hospital readmission. For example, failure to diagnose T2DM at the time of admission to hospital or acknowledging T2DM during discharge proved to be associated with increased level of hospital length-of-stay and 30-day readmission.¹⁶⁻¹⁸ Nonetheless, most research studies pertaining to hospitalization do not target T2DM as a primary condition of concern.

Inpatient stay provides an important and frequently missed opportunity to assess and optimise care for patients with T2DM prior to discharge to the ambulatory setting. Numerous studies have reported on a range of effective interventions for patients with T2DM such as glycaemic control^{19,20}, diabetes education^{21,22}, role of medical specialists^{23,24}, medication adherence^{25,26}, healthy lifestyle activities^{27,28} diet and exercise interventions²² as well as substantial empirical evidence of the contribution of social and behavioural factors to functional status and the onset and progression of disease²⁸⁻³⁰.

Results from a Systematic Review (unpublished) undertaken as part of stage one of the REMIT-2-D Project, suggests there is a gap in patient centred in-hospital interventions that deliver a comprehensive and integrated approach to in-hospital care for patients with T2DM through a

combination of the key interventions as referred to above. The REMIT-2-DS2 project for a patient centred in-hospital intervention aims to create a responsive, person-centered system of care which involves clinicians, primary healthcare providers and community services working with each other and with people with T2DM to ensure coordinated, effective and efficient patient care that reflects the whole of a person's health needs.

We will address this gap, focussing on assessing the validity and effectiveness of a comprehensive treatment package that includes:

- Health literacy (diabetes education for patients, families, patient self-care education and support)
- Psychosocial and social determinants (individual's lifestyle, food related behaviours, socio-economic status and disadvantage)

The implementation of in-hospital treatments for T2DM will, through better coordination and continuity of care, enhance the quality of care for patients by improving health outcomes, promoting patient safety, increasing patient satisfaction, and optimising the use of resources. From a patient's perspective, the treatments will aim to meet both their health and social needs, taking these as the starting point for redesigning their care, and making it an easier journey for the patient throughout their treatment.

3. AIM OF STUDY/RESEARCH QUESTIONS

The aim of this study is to:

- Implement and rapidly optimise an effective, culturally appropriate, in-hospital treatment for patients admitted to the LMH, TQEH and RAH with T2DM.
- Determine whether a treatment package targeted at people admitted to LMH, TQEH and RAH and who have T2DM will improve glycaemic control at 6 weeks and reduce hospital admission or if re-admitted, reduce length of stay.

HYPOTHESIS

Primary Hypothesis

An In-hospital intervention in an Australian public hospital context for people identified as having T2DM, will lead to improvements blood sugars and reductions in diabetes related distress, and ultimately a lower probability of re-admission or if admitted and an admission of shorter duration.

4. STUDY DESIGN

In stage 1 of REMIT-2-D, a Participatory Action Research, informed by the systematic review and stakeholder input was utilised to develop a set of potential in-hospital treatments with specific consideration for the needs of Aboriginal and Torres Strait Islander (ATSI) patients¹⁷. These will be implemented in parallel and compared against a standard-of-care control by a "drop-the-loser design" to determine the optimal intervention. Drop-the-loser designs are a novel methodology for trial design that rapidly identify promising treatments, for example when several promising new treatments exist and there are relatively few patients to test them.

5. STUDY LOCATION

- Lyell McEwin Hospital, SA
- SA Department for Health and Ageing (e.g. centrally held data)

- The Queen Elizabeth Hospital
- The Royal Adelaide Hospital

6. STUDY POPULATION AND SETTING

The participants will be drawn from patients admitted to the Lyell McEwin The Queen Elizabeth (TQEH) and Royal Adelaide (RAH) hospitals in Adelaide, South Australia with Type 2 Diabetes Mellitus (T2DM).

We anticipate randomising 5 patients per week aiming to complete the study in the first quarter of 2020.

7. ELIGIBILITY CRITERIA

a. Inclusion criteria

1. Non-Indigenous and Indigenous peoples of age 18 years and over.
2. Patients with Type 2 DM admitted to LMH, TQEH and RAH

b. Exclusion criteria

1. Non-Indigenous and Indigenous peoples under the age of 18 years.
2. Women who are pregnant.
3. Patients unable to give informed consent.
4. Patients scheduled for coronary angiography

8. STUDY OUTCOMES

a. Quantitative

i. Primary Outcome

- Improved blood sugar control measured by HbA1C at 6 weeks

ii. Secondary Outcome(s)

- a. Change in triglyceride and diabetes distress at 6 weeks
- b. Reduction in readmission to hospital or if re-admitted, a reduction in length of stay
- c. Relationship of psychosocial, environmental and health related factors to the effect of the intervention.

9. STUDY PROCEDURES

a. Recruitment of participants

Patients admitted to the Lyell McEwin hospital, The Queen Elizabeth Hospital and Royal Adelaide Hospital with Type 2 Diabetes Mellitus (T2DM) will be enrolled.

Advertising material may be distributed in the Hospital wards to inform potential participants of the trial (Appendix 1).

b. Study procedures

Care Coordinator role:

- Ask resident, registrar or nursing staff on the general medical and endocrine wards each weekday morning to identify any patients with Type 2 Diabetes and approach them to ask if the care coordinator can talk to them about the study.
- Approach identified patients to deliver information about study and gain consent
- Randomise patients to 1 of 4 groups (study group control 1 or study group intervention 2, 3 or 4). (Figure 1)
- Help patients to complete questionnaires (includes clinical, psychological, knowledge, literacy, access to appropriate health services and medical history) which should mostly take 1.5 hours. However, this may take 2-4 hours as the Care Coordinator will need to balance the need for timely completion of study processes with the need to provide support and understanding, respond to questions and engage in discussion that aims to improve health literacy and reduce diabetes related distress in accordance with the study procedures. If this is tiring for patients the Care Coordinator will ask patients if they would like to stage the process, further patients may request that they do not complete all the questionnaires.
The study care coordinator will also collect some extra medical data from the medical records
Ask patients if they would like a friend or relative with them and/ or, for Aboriginal patients, an Aboriginal health worker.
- Make a time for the Care Coordinator to return to deliver the randomisation intervention allocation. (Figure 1) Ask patients if they would like a friend or relative with them and/or, for Aboriginal patients, an Aboriginal health worker.

The questionnaires include the following (Figure 1) and will be site specific:

The Lyell McEwin Hospital

- Active Australia²⁶
- Diabetes Distress Scale²⁷
- Free Sugar Intake Behavior
- Fruits and Vegetables²⁸
- General Practitioner information
- Medical Patient data
- Patient Health Questionnaire (Depression) ⁹²⁹
- Coping Index ³⁰
- Coping self-efficacy index³¹
- Health literacy: Newest Vital sign UK³²
- Perceived Diabetes self-management ³³Pittsburgh Sleep Quality Index³⁴

The Queen Elizabeth and Royal Adelaide Hospitals

- Active Australia²⁶
- Diabetes Distress Scale²⁷
- Fruits and Vegetables²⁸
- General Practitioner information

- Medical Patient data
- Patient Health Questionnaire (Depression) 9²⁹
- Coping self-efficacy index³¹
- Health literacy: Newest Vital sign UK³²
- Perceived Diabetes self-management ³³

IN-HOSPITAL TREATMENT PACKAGE FOR T2DM PATIENTS

There are 5 educational resources to develop diabetes-related health literacy. These were developed from a systematic review of the evidence and a series of focus groups with health professionals and consumers.

Study educational resources for diabetes -related health literacy (Appendix 3)

1. Diabetes self-care
2. Eat Whole Foods
3. Good sleep = Good health
4. Muscle resistance activity
5. Coping with diabetes to reduce diabetes distress

In addition, Diabetes Australia has produced several health literacy fact sheets freely available on the National Diabetes Service Scheme (NDSS) website: <https://www.ndss.com.au/>

1. NDSS_Understanding Type 2 Diabetes³⁵
2. NDSS_Healthy Food Choices³⁶
3. NDSS_Physical Activity³⁷

The randomisation study groups are as follows (Figure 1):

Study group 1:

Standard factsheets from the Diabetes Australia Foundation (NDSS) on **Understanding T2 diabetes, Healthy Food Choices and Physical Activity**

Study group 2:

Study_Self-care, Coping, Sleep, and **NDSS_Healthy Food Choices**

Study group 3:

Study_Self-care, Coping, Sleep, and **Study_Eat whole foods and NDSS Physical activity**

Study group 4:

Study_Self-care, Coping, Sleep AND **Study_Eat whole foods and Study_ Muscle resistance activity.**

It is estimated that it will take 30 mins for the Care Coordinator to deliver these education resources to the participant.

Six-week follow-up visit

Two-three weeks post discharge from hospital the he Care Coordinator will post a pathology request form for the 6-week blood test. At 6 weeks the patient will receive a phone call from the Care Coordinator to conduct the 6-week Diabetes Distress scale questionnaire over the phone and ask whether they have had a blood test done. If not, they will receive another phone call from a blood collection nurse (study

coordinator, [name]) requesting an appointment to visit the patient's home to collect the blood sample. At the home visit the study coordinator will also present some information about other clinical trials that maybe of interest to the patient. However, the patient is under no obligation to participate. y. In the event that the patient cannot be contacted by phone we will write to them and include an accompanying Diabetes Distress Scale questionnaire and a reply-paid envelope.

Based on the 6-week HbA1C results, the 2 study groups from 2, 3 and 4 with the least change in HbA1C from baseline will no longer be followed (called 'drop the loser') with the remaining study group left to compare with study group 1.

The HbA1C and triglyceride blood test at 6 weeks is part of normal routine practice and therefore billed to Medicare.

c. Access to Existing Data

Patient medical records including enrolled patient's HbA1C and triglyceride blood tests.

d. Data Linkage Management

Data linkage methods will be required to link enrolled patient blood test results and admission data to readmission and length of study data from the SA Health Integrated South Australian Activity Collection (ISAAC. This is of interest in the 12-month period following the patients index admission and subject to further funding.

i) Privacy and Confidentiality

- A random unique patient identifier will be created and appended to the linked data file
- The following potentially identifying data items will be dropped:
 - o Medicare Number/IRN
 - o Date of birth (replaced with the calculated field age)
 - o Hospital URN
 - o Separation date/time and admission date/time (replaced by length of stay hours)

ii) During the Project

The research and questionnaire data of participants will be recorded in an Adelaide University REDCap (Research Electronic Data Capture) database, identified by a unique study number only. Participant identifying information will be recorded on a separate spreadsheet and stored on a password protected computer, accessible only to study staff for the 6-week follow-up visit.

The data analysts will discuss options with the data custodians to ensure that separation of data is managed appropriately such that individuals will only have access to the information needed to perform their role i.e. those involved in linking the datasets only see the identifying information to create the links between different datasets; while those involved in analyzing the integrated data only have access to de-identified data specific to the project requirements.

The de-identified data files will be stored on and accessible from an encrypted USB drive and will be kept in a locked drawer when not in use.

iii) After the Project

The original data files will be archived on an encrypted USB drive at Adelaide University and stored in a safe until for five years and subsequently destroyed.

e. Safety considerations

Privacy and protection of identifiable data will be managed as above. In the delivery of the interventions, any issues raised by enrolled patients with the Care Coordinator will be supported with a process of medical assessment.

f. Data monitoring

The Principal Investigator and the REMIT-2-D Project Expert Advisory Group (**Appendix 2**) will be responsible for the monitoring and review of data collection and storage, including the review of data protocols and associated agreements.

The researchers will provide regular reports to the Expert Advisory Group regarding the use of the data and will immediately report any potential breaches.

In addition, the University of Adelaide owns any data that is generated from the study, owns the protocol and administers the grant funding. [name] the CPI is employed by University Adelaide.

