11. DATA HANDLING AND RECORD KEEPING

a. Data Collection and Management Responsibilities

- Screening, recruitment, consenting, delivery of interventions and data collection will be conducted by a trained Care Coordinator and is resource at 1 FTE for 8 months.
- Intervention formatting, ethical, financial, human resource, data management and assistance with 6 week phone follow-ups if required will be conducted by a Project Manager and is resourced at 0.8 then 0.4 FTE for 12 months.
- The expert advisory group will oversee all study processes, study reports and supervise study design and outcomes.

b. Study Records Retention

The Principal Investigator will maintain all records pertaining to this study for a period of 15 years from the date of publication.

University of Adelaide records, once created and captured, must not be damaged, altered or destroyed other than in accordance with General Disposal Schedules No 24 - South Australian Universities or an alternative Disposal Schedule, and with authorisation from the University Archivist or delegate in consultation with relevant business owners.

Responsibility: All employees, titleholders, consultants, contractors and volunteers of the University of Adelaide must:

- a. Create records that adequately document the activities and decisions of the University in which they take part, whether related to learning and teaching, research, commercialisation or administration;
- b. Capture important business records into the University recordkeeping system or an alternative business system with functionality to retain records in a secure manner for as long as they are legally required;
- c. Take appropriate steps to ensure the reliability of University records and ensure records can be located;
- d. Manage security of University records or restrict access if appropriate;
- e. Ensure records are described adequately to allow the University to store, dispose and/or archive them in accordance with academic, business and legal requirements; and
- f. Comply with legal requirements and standards including the State Records Act 1997, State Records Adequate Records Management Standards and the Australian Standard AS ISO 15489, as well as the University's procedures and processes in relation to records management.

c. Protocol Deviations

A protocol deviation is any noncompliance with the study protocol, Good Clinical Research Practice, or HREC requirements.

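### Baseline questionnaires are listed after randomisation and combined with supportive discussion, and the role that delivers the education also takes the 6-week distress score, so the distress and effect-modifier results are open to avoidable bias

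*Protocol*

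**What the plan says.** Protocol section 9.b (Care Coordinator role) gives a list of tasks. After the patient has been approached and has consented, the next item is "Randomise patients to 1 of 4 groups (study group control 1 or study group intervention 2, 3 or 4". The item after that is "Help patients to complete questionnaires (includes clinical, psychological, knowledge, literacy, access to appropriate health services and medical history"; the forms named include the Diabetes Distress Scale, a depression questionnaire, and health literacy and self-management measures. Patients may ask not to complete all of them. The list ends with "Make a time for the Care Coordinator to return to deliver the randomisation intervention allocation".

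The questionnaires should mostly take 1.5 hours. The protocol adds: "However, this may take 2-4 hours as the Care Coordinator will need to balance the need for timely completion of study processes", weighed against giving support, answering questions and the instruction to "engage in discussion that aims to improve health literacy and reduce diabetes related distress in accordance with the study procedures". No arm is singled out or exempted. Delivery of the randomised material is put at 30 minutes.

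For follow-up, section 9.b states: "At 6 weeks the patient will receive a phone call from the Care Coordinator to conduct the 6-week Diabetes Distress scale questionnaire". A postal form with a reply-paid envelope is the fallback for patients who cannot be reached. Section 11.a gives screening, consent, delivery and data collection to the Care Coordinator, and says that "assistance with 6 week phone follow-ups if required will be conducted by a Project Manager".

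Section 8 makes the change in distress part of secondary outcome a, and the relationship of psychosocial and other factors to the intervention's effect secondary outcome c. Reduced distress is also part of the primary hypothesis in section 3.

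**The concern.** A baseline measure should be fixed before anyone involved in taking it can know the allocation. Here the listed order puts it afterwards, with help from the person who did the randomising. Three things follow.

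- **Baseline values and missing forms.** Help, emphasis and encouragement to finish the forms can vary with the arm, so both the recorded values and which forms are missing can depend on allocation.
- **Measurement mixed with intervention.** Discussion meant to lower distress takes place in the session in which baseline distress is recorded. The score may then reflect the discussion rather than the patient's state on entry.
- **Follow-up rating.** Distress at 6 weeks is self-reported, by phone, to the role that delivered the education. Patients may give answers that please, and the rater knows the arm.

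At stake are the distress comparison and the search for factors that modify the effect. Both rely on baseline questionnaires. These are matters of how data are collected, so an analysis plan could not undo them.

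**Working it through.** **1. Order of steps.** Set side by side, section 9.b reads: consent; randomise; assisted questionnaires; return to deliver the allocation. The last step presupposes an allocation already made and follows the questionnaires in the list, so it agrees with that order. No other section places the questionnaires before randomisation.

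**2. Who knows the arm, and when.** At 6 weeks the coordinator role has already delivered arm-specific material, so the arm is known. At baseline, knowledge is an inference: the coordinator randomises and so presumably sees the result. The protocol does not say when the patient is told. It mentions neither blinding nor an independent assessor.

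**3. What this does to a change score.** Let D0 and D6 be the recorded distress scores. In each arm, let b0 and b6 be the mean errors that the measuring conditions add to them. Then

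observed between-arm difference in (D6 − D0) = true difference + [b6(exp) − b6(ctl)] − [b0(exp) − b0(ctl)].

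- If the baseline discussion shifts D0 equally in all arms, the last bracket is zero and the between-arm contrast is unharmed. Only the within-arm change from baseline is distorted.
- If the shift differs by known allocation, the last bracket does not vanish. More supportive discussion in an experimental arm would lower D0 there and make its improvement look smaller.
- If patients in an experimental arm answer more favourably at 6 weeks, the first bracket is negative and improvement looks larger.

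The two errors can oppose each other, so the direction of the net bias is not known. Randomisation before baseline is what allows b0 to differ by arm; with baseline first, that bracket is zero in expectation. The same holds for missing baseline forms.

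**4. Time in the session.** Inputs, all from section 9.b: 1.5 h usual, 2 to 4 h when extended, 0.5 h for delivery. The extension linked to support, questions and discussion is 2 − 1.5 = 0.5 h to 4 − 1.5 = 2.5 h, which is 1 to 5 times the 0.5 h delivery. In the usual 1.5 h case there is no extension. This is an upper bound on discussion time, since it includes answering questions.

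**5. Primary outcome.** The stated 90% power is not in dispute. It was simulated as a two-stage drop-the-loser design with 33 × 0.8 = 26.4 evaluable patients per arm per stage, one arm at 0.6 SD and the others at 0. The critical value was about 1.64, set for 10% one-sided error. Power is 91.3%, or 90.7% if the effective arm must also be the one kept. HbA1c is a laboratory value and alone decides which arms are dropped, so neither the selection nor the final test passes through a rater.

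**The case against.** **The order is read from an unnumbered list of tasks.** This is true, and the flow chart it cites could not be seen in the text reviewed. If practice is different, the text still needs correcting. The mixing of discussion with measurement and the 6-week rating do not depend on the order.

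**Equal contact in all arms can serve as attention control.** This has force. The discussion is not confined to any arm, and the words "engage in discussion that aims to improve health literacy and reduce diabetes related distress in accordance with the study procedures" leave open whether it is common or arm-specific. If it is truly common, it does not favour an arm. The protocol does not secure that, because the person holding the discussion is the one who has randomised.

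**Patients may decline forms in any order.** Also true, and the protocol mentions that the session may be tiring. But forms declined before randomisation cannot depend on allocation.

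**This is an early-phase trial and only secondary measures are touched.** That limits the weight of the point but does not remove it.

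A reader might go further and infer that the control arm is in effect treated and that the HbA1c comparison loses power. The documents do not support this. Controls receive education by design, in the form of standard factsheets. All arms have the same session, and an effect that adds equally everywhere leaves the difference unchanged. Dilution needs overlap between the discussion and the package, or a ceiling, and the documents give no figure for either. Nor is the whole 1.5 to 4 h session (3 to 8 times the delivery time) coaching, since most of it may be form-filling.

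**Conclusion.** The point holds for secondary outcomes a (its distress component) and c. As written, baseline questionnaires follow randomisation, supportive discussion takes place while they are completed, and one role both delivers the education and records distress at 6 weeks. Both ends of the distress change score are thus exposed to avoidable bias, of unknown size and uncertain direction.

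The conclusion rests on reading the list as a sequence and, for baseline only, on the coordinator seeing the allocation when randomising. Knowledge of the arm at 6 weeks follows from the text. The primary outcome is not reached by assessor bias, the stated power stands, and any dilution of the HbA1c contrast cannot be sized from the documents. The change should be made, but it is not a threat to the trial's main test.

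**What to change.** Rewrite section 9.b in this order: consent; baseline questionnaires and record extraction; randomisation; delivery of the package. Make the flow chart agree. Limit the questionnaire session to neutral clarification and support, set out in a short script, and keep educational discussion for the delivery session.

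Where feasible, have the 6-week distress scale self-completed, or taken without sight of allocation by the Project Manager, who is already named for help with the 6-week calls. Keep the Care Coordinator's call in any case: it asks about the blood test and leads to the home visit, so replacing it by post could lose primary-outcome data.

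The cost is revised text, a script and some calls moved to the Project Manager. That role also covers intervention formatting and data management, so access to allocation would have to be restricted for these calls. Patients know what education they received and can still answer favourably to anyone, so the last step reduces the follow-up bias without removing it. Arms, sample size and outcomes are unchanged.
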